	
in each treatment group to have 90% power of detecting this difference at the 5% level of significance in the presence of a 30% dropout rate.
 
Prospective observational arm The number of patients in the non-randomised part (observational arm) is not pre-defined because no formal statistical endpoint will be tested.

Inclusion criteria
	
Both arms Eligible patients have to provide written informed consent and must be able to understand and be willing to sign the written informed consent. Entry in the study is defined as the signing of the informed consent.
 
 
• Established histological diagnosis of a malignant primary or metastatic tumour;
 
• Histologically, radiologically or scintigraphically proven spinal metastasis;
 
• Age <math>\geq 18</math> years old;
 
• Karnofsky performance status <math>\geq 60\%</math>.
 
• Life expectancy <math>\geq 1</math> year according to investigator`s estimate
 
 
Randomised arm
 
 
• Osteolytic or mixed osteolytic/osteoblastic lesion
 
• Pain in the affected spinal region
 
• Willingness to undergo randomisation
 
•
 
 
Prospective observational arm
 
 
• Purely osteoblastic lesions or no pain in the affected spinal region or unwillingness to undergo randomisation
 

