Statistics	
Randomised arm
 
Sample size
 
160 participants will be recruited to the study. Based on prior research, a 40% pain response rate (<math>\geq 2</math> point improvement based on VAS) is expected in the standard treatment group and a 30% difference in pain response is expected between groups. At least 80 patients are needed in each treatment group to have 90% power of detecting this difference at the 5% level of significance in the presence of a 30% dropout rate.
 
Statistical analysis
 
Statistical analysis will be done in three populations: 1) Intent-to-Treat population (ITT) including all patients who were randomised and received at least one fraction of radiation therapy; 2) Per Protocol population (PP) including all patients of the ITT who have received study treatment according to randomisation without significant protocol violations and 3) safety-analysis set including all patients who were randomised and received at least one fraction of radiation therapy. To compare long-term pain control, Pearson's chi-square test with a continuity correction will be used on pain response rates across the two

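### The stated 90% power does not hold for the continuity-corrected chi-square test that the protocol specifies: at the assumed 30% dropout it is about 86%

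*Protocol*

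**What the plan says.** The Protocol Synopsis, under Statistics (Randomised arm, Sample size), expects "a 40% pain response rate" on standard treatment and says that "a 30% difference in pain response is expected between groups". It concludes: "At least 80 patients are needed in each treatment group to have 90% power of detecting this difference". The claim is made for a significance level of 5% and for a dropout of 30%. The Number of patients entry gives the same figures. Neither place names the test or formula behind the 80, or says whether the 5% is one- or two-sided.

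The next paragraph of the Statistics entry, on statistical analysis, fixes the primary comparison as Pearson's "chi-square test with a continuity correction will be used on pain response rates" in the two arms.

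**The concern.** A continuity correction shrinks the test statistic, so a corrected chi-square test needs more patients than an uncorrected one for the same power. A sample size worked out without the correction therefore falls short when the correction is applied at analysis. The protocol fixes both the power and the test, so this is a disagreement between two of its own statements and not a detail left for a later analysis plan.

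At stake is the probability of missing the effect the trial was designed to find. That probability is presented as 10%, on the condition of 30% dropout.

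**Working it through.** **Inputs, all from the Synopsis.** Control response 0.40. Difference 0.30, read as absolute, so 0.70 on SBRT. Level 0.05, taken as two-sided because a chi-square test is two-sided. Power 0.90. Allocation 1:1. 80 per arm with 30% dropout, so 80 × 0.7 = 56 evaluable per arm.

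**1. Reproduce the plan's figure (no correction, pooled variance under the null).**
n = [1.96 × √(2 × 0.55 × 0.45) + 1.2816 × √(0.40 × 0.60 + 0.70 × 0.30)]² / 0.30²
= [1.96 × √0.495 + 1.2816 × √0.45]² / 0.09 = 55.7, so 56 evaluable.
56 / 0.7 = 80 randomised per arm, which matches exactly.

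**2. Try other routes to 80.**

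| Formula | Evaluable per arm | Randomised per arm, n/0.7 |
|---|---|---|
| Uncorrected, two-sided | 56 | 80 |
| Arcsine, uncorrected, two-sided | 56 | 80 |
| Unpooled, uncorrected, two-sided | 53 | 76 |
| Uncorrected, one-sided | 46 | 66 |
| Corrected, one-sided | 52 | 75 |
| Corrected, two-sided | 63 | 90 |

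The only corrected route that comes close multiplies by 1.3 instead of dividing by 0.7: 63 × 1.3 = 81.9, so 82. That is not 80, and it under-allows for dropout.

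**3. Sample size for the specified test.**
n_c = (n/4) × [1 + √(1 + 4/(n × 0.30))]²; with n = 55.7 this is 62.2, so 63 evaluable. 63/0.7 = 90 randomised per arm.

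**4. Power of the specified test with 56 evaluable per arm, normal approximation.**
Null standard error: √(0.495/56) = 0.0940. Alternative standard error: √(0.45/56) = 0.0896.
- Uncorrected: Φ[(0.30 − 1.96 × 0.0940)/0.0896] = 90.2%.
- Corrected (difference reduced by 1/56 = 0.0179): Φ[(0.30 − 0.0179 − 1.96 × 0.0940)/0.0896] = 86.2%.

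**5. The same by exact enumeration.** Sum the probabilities of all pairs of Binomial(n, 0.40) and Binomial(n, 0.70) outcomes for which the statistic exceeds the 5% chi-square critical value.

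| Evaluable per arm | Dropout from 80 | Uncorrected | Corrected |
|---|---|---|---|
| 56 | 30% | 89.6% | 85.7% |
| 60 | 25% | 92.4% | 89.4% |
| 61 | about 24% | 93.1% | 90.2% |
| 64 | 20% | 93.3% | 90.4% |
| 80 | 0% | 97.1% | 95.9% |

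The corrected test first reaches 90% at 61 evaluable. 61/0.7 = 87.1, so 88 randomised per arm.

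**6. Actual two-sided size with 56 per arm**, by the same enumeration with equal rates in both arms: about 4.6% to 5.2% without the correction for common rates from 0.2 to 0.8, and about 3% with it.

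**The case against.** The strongest reply is that little turns on this. The loss is about 4 percentage points of power in one planning scenario, and the corrected test errs on the safe side, so no false claim of benefit can come from the mismatch. The loss also shrinks quickly if retention is better than assumed: at about 24% dropout the specified test already has 90.2% power, and with no dropout 95.9%. All of that stands, and it keeps the point below critical. It does not remove it, because the protocol makes its 90% claim explicitly under 30% dropout, and there the claim is not met for the specified test.

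Three stronger readings are tempting, and the document does not support them.

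- A reader might infer that the sponsor demonstrably computed power for the uncorrected test. The exact match makes that likely, but no formula is stated, so it remains an inference. The shortfall does not depend on it: however 80 was obtained, 30% dropout leaves 56.
- A reader might infer that the correction serves no purpose. The uncorrected test slightly exceeds 5% at some response rates, so giving up power for stricter control of the level is a legitimate choice, provided that the stated power reflects it.
- A reader might infer that the corrected p-value will contradict the planned interval for the risk difference. That depends on the interval method. The protocol names Wilson only for the rates within each arm and no method for the difference, so nothing can be concluded.

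**Conclusion.** The point holds as a mismatch between the stated power and the specified test. With 30% dropout the planned corrected test has about 86% power (85.7% exact, 86.2% by normal approximation), not 90%. The risk of missing a true 40% versus 70% difference is 14.3%, against 10.4% for the uncorrected test by the same exact standard.

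This rests on three readings: the 30% is an absolute difference, the 5% is two-sided, and dropouts contribute no outcome and fall equally on both arms. The first two are the readings under which 80 is reproduced exactly. It should be fixed, but it is not critical: the trial remains valid and its results interpretable under either test.

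**What to change.** Choose one of two options and document it before the primary comparison is analysed.

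1. **Remove the continuity correction from the primary test.** Test and sample size then agree: 56 evaluable per arm give 90.2% by the formula and 89.6% exactly. The cost is one sentence, with no extra patients or data. The downside is small but real. It changes a pre-specified test to a less conservative one in an open-label trial whose enrolment was scheduled from 2016 and which has a conditional interim efficacy analysis. The amendment should therefore give its reason and its timing relative to any look at outcome data. Actual size can reach about 5.2% at some rates.
2. **Keep the corrected test and restate the power** as about 86% under 30% dropout, in both the Number of patients and the Statistics entries. This leaves the conduct and analysis of the trial unchanged.

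Whichever is chosen, state the formula, the sidedness and the dropout adjustment behind the sample size. Keeping both the correction and 90% power would take about 88 to 90 randomised per arm, or 176 to 180 in total. That is 16 to 20 patients more than the planned 160, and neither option above needs them.

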
Study procedures
	
Both arms Informed Consent Prior to any study specific measures (including screening measures), patients must sign the informed consent form, after nature, scope, and possible consequences of the clinical study have been explained to them in a form understandable for them.
 
Both arms Screening All patients are screened for eligibility before treatment allocation. The following will be assessed:
 
 
• Review of eligibility criteria;
 
• Medical history;
 
• Physical and neurological examination;
 
• Height, weight, vital signs, Karnofsky performance status;
 
• Recording of all preexisting symptoms;
 
• Recording of pain and pain medications;
 
• Recording of concomitant medications;
 
• Radiology:             
 
○ CT scans;
 
○ MR scans;
 
○ Bone scans or positron-emission tomography scans;
 
 
 
• Pregnancy test for women of child bearing potential;
 
• Decision of a study centre tumour board on radiation therapy for painful spinal metastases;
 
• Health-related QoL as measured by the EORTC QLQ-C15-PAL, EORTC-BM22 and EQ-5D-5L patient reported questionnaires;
 
• Willingness to undergo randomisation
 
 
Randomised arms Treatment phase Patients will be treated according to arm A (investigational treatment) or arm B (standard treatment).
 
In arm A, patients immobilized in treatment position will undergo planning CT and MR. Two planning target volumes (PTVs) will be determined on CT and MR as follows: 1) the high-dose gross tumour

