	
treatment arms. Wilson-method 95% confidence intervals will be provided for the pain response rate in each treatment group. The risk difference and its confidence interval will be provided as an effect measure, easily allowing for readers to calculate the 'number needed to treat'. Additionally, the odds ratio will be provided as a second effect measure. This measure allows for easy extension to logistic regression if other characteristics vary greatly across treatment groups. If daily oral morphine equivalent or epidural involvement vary greatly across treatment groups, a logistic regression model including treatment, daily oral morphine equivalent, epidural involvement, and centre will be used, which yields an odds ratio and its 95% confidence interval to summarize the difference in pain response between the treatment groups while controlling for other factors.
 
The Kaplan Meier estimator will be used for overall survival across the two treatment groups. (Semi-) Competing risk methods will be used to address the following events: local metastasis recurrence, cancer-specific death, and death by other causes. Cumulative incidence functions and sub-distribution hazards accounting for competing risks will be computed.
 
All safety analyses will be conducted on the safety-analysis set according to treatment received. For pre-specified protocol specific AEs, the point estimate of the difference between treatment arms, with 2-sided 95% CIs, will be provided. All other safety analyses will be presented in tabular format with the appropriate summary statistics for each treatment arm. QoL descriptive analysis will include the subset of the PP patients.
 
Prospective observational arm
 
Sample size
 
The sample size will not be pre-defined since no formal statistical hypothesis will be tested. For the University Hospital Zurich, we assume ca. 40 patients.
 
Statistical analysis
 
The statistical analysis will be mainly descriptive and exploratory. We report mean and standard deviation for continuous variables and median and interquartile range for ordinal variables and number and percentage for categorical variables. For the primary outcome, the proportion of patients with clinically relevant pain reduction will be estimated with Wilson 95% confidence intervals. Kaplan Meier curves will be plotted for overall survival. Competing risk methods will be used for local metastasis control, cancer-specific survival, and overall survival. Descriptive statistics will be used to describe quality of life outcomes and safety outcomes.
 
Interim Analysis
 
If the trial fails to recruit at least 50% of the initially planned patients in the randomised arms until 12/2020 (originally planned recruitment end), an interim safety and efficacy analysis of both randomised and prospective observational arms will be conducted.
 
If no safety concerns are raised after this interim analysis and there is a clinically relevant benefit of at least 10% for the experimental regimen

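### The adjusted analysis depends on an undefined imbalance trigger, omits baseline pain, and brings in the stratification factor only if the trigger fires

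*Protocol*

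**What the plan says.** The Statistics row of the Protocol Synopsis (Randomised arm, Statistical analysis) names Pearson's chi-square test with a continuity correction for the pain response rates. The risk difference and its confidence interval are the effect measure, and the odds ratio is a second one. Of the odds ratio it says: "This measure allows for easy extension to logistic regression if other characteristics vary greatly across treatment groups". It then becomes specific: "If daily oral morphine equivalent or epidural involvement vary greatly across treatment groups, a logistic regression model" containing treatment, morphine equivalent, epidural involvement and centre is to be fitted, giving an adjusted odds ratio with a 95% confidence interval.

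Four other places in the Synopsis bear on this:
- **End-points:** the primary endpoint is a fall of at least 2 points on the pain VAS at 6 months.
- **Inclusion criteria:** the randomised arm requires pain in the affected region, with no minimum score.
- **Study procedures, Screening:** the list includes "Recording of pain and pain medications", so baseline pain and analgesic use are available for everyone.
- **Treatment and Study centres:** centre is the only stratification factor, and 20 sites take part.

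**The concern.** Covariates in a randomised comparison are best chosen in advance for their prognostic value. Here adjustment depends on observed imbalance, which under sound randomisation is chance. With no threshold, two careful analysts could disagree on whether the model is called for. Once it is fitted, nothing says which result leads the report.

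The covariate list is also weak. Someone who starts below 2 points on the VAS cannot respond, so baseline pain bears directly on the outcome, yet it is left out. Centre was used to stratify the randomisation but is ignored unless two other variables happen to be imbalanced.

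At stake are the precision of the primary estimate and a clear statement of which estimate is primary.

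**Working it through.** **1. The plan's own sample size.** Inputs from the Statistics row: "a 40% pain response rate" on standard treatment, "a 30% difference in pain response is expected between groups" (so 40% v 70%), "to have 90% power of detecting this difference", "at the 5% level of significance" (taken as two-sided) and "in the presence of a 30% dropout rate".

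n per arm = [1.960·√(2·0.55·0.45) + 1.282·√(0.40·0.60 + 0.70·0.30)]² / 0.30² = (1.379 + 0.860)² / 0.09 = 55.7, so 56 evaluable. Then 56/0.70 = 80 randomised. The stated figure reproduces, and the analysis rests on about 112 evaluable patients.

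**2. How often would the trigger fire by chance?** A standardised difference between arms has SE √(2/56) = 0.189. For threshold d, one covariate exceeds it with probability p = 2[1 − Φ(d/0.189)], and at least one of two independent covariates with probability 1 − (1 − p)². At d = 0.25, p = 0.186 and 1 − 0.814² = 0.34.

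| Threshold | 0.10 | 0.20 | 0.25 | 0.30 | 0.50 |
|---|---|---|---|---|---|
| Trigger fires | 84% | 50% | 34% | 21% | 2% |

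The unstated threshold therefore largely decides whether the adjusted model is reported.

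**3. Power at 40% v 70%.** Simulation with 56 per arm and 6,000 trials per setting. The protocol gives no prognostic strengths, so these are assumed: log-odds −0.5 per SD of morphine equivalent, −0.5 for epidural involvement (40% prevalence), and 0, 0.5 or 1.0 per SD of baseline pain. The models in this table leave out centre.

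| Analysis (power, %) | 0 | 0.5 | 1.0 |
|---|---|---|---|
| Planned corrected chi-square | 86.15 | 85.42 | 86.58 |
| Uncorrected chi-square | 89.97 | 89.22 | 90.22 |
| Logistic, morphine + epidural | 91.85 | 91.22 | 91.65 |
| The same + baseline VAS | 91.67 | 92.48 | 95.00 |

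Row differences split the gap to the planned test:
- Removing the continuity correction: 3.82, 3.80 and 3.64 points.
- Always adjusting for morphine and epidural involvement: 1.88, 2.00 and 1.43 points.
- Adding baseline VAS: −0.18, 1.26 and 3.35 points, that is about 0, 1 and 3.

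Under the conditional rule, power is 86-91% for thresholds from 0.50 down to 0.10.

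**4. Type I error.**
- Trigger followed mechanically, centre left out, thresholds 0.10 to 0.50: 2.9-4.8%.
- Logistic with morphine, epidural involvement and 20 centre dummies, always fitted: 7.53%, 7.17% and 7.77% at the three baseline-pain strengths. Two further sets of runs gave 6.6-8.4% (with assumed centre effects of SD 0.5 and 1.0) and 5.9-7.2%. Overall this is about 6-8%. The average centre contributes 112/20 = 5.6 evaluable patients.
- Reporting whichever of the corrected chi-square or the centre-dummy model is significant: 6.7-8.7%, against 6.6-8.4% for the dummy model alone in the same runs. Choosing adds at most 0.3 points.
- The same choice with the model available only above a standardised difference of 0.25: 3.3-5.4%.

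**The case against.** The strongest defence is that the primary analysis is fixed. The test and the risk difference are stated without condition, and the logistic model is introduced as an extension of a second effect measure. The corrected chi-square is most naturally read as always performed, and an unadjusted test is valid in a randomised trial. This stands, and it confines the ambiguity to the status of the adjusted odds ratio.

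A second defence is that a threshold is detail for a statistical analysis plan, which may exist but is not shown. That is fair for the threshold alone. It does not cover the rule itself: the protocol fixes that adjustment depends on observed imbalance and fixes a covariate list without baseline pain.

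Three stronger readings are tempting but unsupported:
- *Choosing between two results after seeing the data inflates the false-positive rate.* The rates above 5% come from the centre dummies, and the choice adds almost nothing. A free pick that also included an uncorrected chi-square reached about 6%, but the plan does not offer that test.
- *Baseline pain would recover the whole gap to the planned test.* Between 3 and 4 points of that gap belong to the continuity correction, a separate issue, and the share of baseline pain depends on an assumed strength.
- *The morphine covariate could be a post-treatment dose, or balance will be judged unblinded.* The text does not date the covariate, but checking arms for imbalance implies a baseline value. The trial is open-label, but the text does not say who judges balance. Dating the covariate is a clarification.

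**Conclusion.** The point holds as a worthwhile improvement and does not threaten validity. Adjustment hangs on an undefined imbalance trigger, a recorded covariate that limits the outcome is omitted, and the stratification factor is used only by accident of the trigger.

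The gain from baseline VAS is about 0, 1 and 3 points of power at assumed strengths of 0, 0.5 and 1.0 log-odds per SD. Always adjusting for the two listed covariates gives roughly 1.5 to 2 more under the assumptions above. The trigger rule itself does not inflate type I error. The listed model can, at about 6-8%, if centre means 20 fixed dummies. That is an assumption, because the protocol names centre without a method and the number of centres contributing evaluable patients is unknown.

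The 92-95% power for the model with baseline VAS was obtained without centre, so it is a guide to the recommended analysis and not its exact operating characteristic.

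**What to change.** Delete the imbalance trigger, including the open-ended reference to other characteristics. Always fit one prespecified logistic model with treatment, baseline VAS, pre-treatment daily oral morphine equivalent and epidural involvement. Name the method for centre: a random effect, pooling of small centres by a stated rule, or a stratified method, but not 20 fixed dummies.

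From that model report the covariate-standardised risk difference with its 95% confidence interval beside the odds ratio. This keeps the risk difference as the effect measure already planned. State which analysis is primary, and give the unadjusted comparison as support.

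The cost is wording and a little analysis work. Baseline pain and pain medication are already recorded at screening, so no new data are needed.

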Study type/design	
This is an international, multicentre, randomised, open-label, prospective, controlled study. This study additionally includes a prospective observational arm for patients not eligible for randomisation who are treated in analogy to arm A of the randomised arm.

Primary objective	
Randomised arm To compare long-term pain response after dose-intensified image-guided hypofractionated SBRT employing SIB versus conventional radiation therapy for painful spinal metastases.
 
Prospective observational arm To assess the long-term level of pain after dose-intensified image-guided hypofractionated SBRT employing SIB

Hypothesis	
Randomised arm Dose escalation for painful spinal metastases using image-guided hypofractionated SBRT provides superior long-term pain response without adding toxicity as compared to conventional radiation therapy.
 
Prospective observational arm To prospectively evaluate safety and efficacy of SBRT for vertebral metastases; no formal statistical endpoint will be tested.

End-points	
Randomised arm Primary end-point:
 
 
• Pain response - improvement by <math>\geq 2</math> points on the pain Visual Analogue Scale at 6 months post-treatment at the treatment site.
 
 
Secondary end-points:
 
 
• Local metastasis control;
 
• Overall survival;
 
• Cancer-specific survival;
 
• Quality of life (QoL);
 
• Acute and late toxicity.
 
 
Prospective observational arm Primary end-point:
 
 
• Pain response - improvement by <math>\geq 2</math> points on the pain Visual Analogue Scale at 6 months post-treatment at the treatment site.
 
 
Secondary end-points:
 
 
• Local metastasis control;
 
• Overall survival;
 
• Cancer-specific survival;
 
• Quality of life (QoL);
 

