	
 
• Acute and late toxicity.
 
 
Both arms  Exploratory end-points:
 
 
• Time interval from patient presentation to start of SBRT;
 
• Central collection of all radiotherapy treatment plans for QA analyses.
 
• Central collection of all follow-up imaging for normal tissue response analyses of the vertebra on CT and MRI imaging to dose-intensified SBRT.
 

Treatment	
Both arms  Stratification by centre.
 
Randomised arm  Patients eligible for the randomised arm will be randomised in a 1:1 ratio to either of the following regimes:
 
Arm A (investigational) – investigational treatment  Image-guided hypofractionated SBRT using SIB to escalate radiation dose in the tumour (high-dose target volume) while maintaining a conventional dose in the un-involved segments of the affected vertebrae (conventional-dose target volume).
 
 
• in the case of no epidural involvement: 40 Gy and 20 Gy in 5 fractions to the high-dose and conventional-dose target volume, respectively;
 
• In the case of epidural involvement: 48.5 Gy and 30 Gy in 10 fractions to the high-dose and conventional-dose target volume, respectively;
 
 
or
 
Arm B (control) – standard treatment  External 3-dimensional conformal radiotherapy aiming at homogeneous irradiation of the affected vertebrae: each centre has to choose one fractionation protocol and use this one consistently within this study
 
 
• 20 Gy in 5 fractions
 
• 30 Gy in 10 fractions
 
 
Prospective observational arm  Patients eligible for the prospective observational arm (free of pain, purely osteoblastic metastases or refusal of randomisation), will be treated according to the investigational arm (arm A) of the randomised arm of the trial.

Number of patients	
Randomised arm  160 participants will be recruited to the study. Based on prior research, a 40% pain response rate (<math>\geq 2</math> point improvement based on VAS) is expected in the standard treatment group and a 30% difference in pain response is expected between groups. At least 80 patients are needed

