--	--

	
 
Health-related QoL as measured by the EORTC QLQ-C15-PAL, EORTC-BM22 and EQ-5D-5L patient reported questionnaires.
 
 
Both arms
 
Follow-up visits
 
Patients will be followed-up for 2 years after treatment completion or until death. Follow-up visits are scheduled at 3, 6, 12 and 24 months (<math>\pm 4</math> weeks) after treatment. The following procedures will be done at every follow-up visit:
 
 
Physical and neurological examination;
 
Weight, vital signs, Karnofsky performance status;
 
Assessment of pre-specified protocol-specific adverse events;
 
Recording of all other adverse events;
 
Recording of pain and pain medications;
 
Recording of concomitant medications;
 
Radiology as clinically indicated for osteolytic lesions, based on institutional protocol: CT and/or MR scans;
 
Health-related QoL as measured by the EORTC QLQ-C15-PAL, EORTC-BM22 and EQ-5D-5L patient reported questionnaires.
 

Study schedule	First quarter Q1 2016 (first patient enrolment) – Q4 2023 (last patient enrolment)
Sponsor-Investigator and Coordinating-Investigator	
[name] [name]          Department of Radiation Oncology          University Hospital Zurich          [name]          [name]          Switzerland          [contact]          [contact]          e-mail: [contact]

Study centres	Currently participating centres: 20 sites in Switzerland and in Europe

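### Quality of life, a secondary end-point, has only the per-protocol set named for its analysis, so the by-arm summary does not compare the groups as randomised

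*Protocol*

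**What the plan says.** The Protocol Synopsis, under End-points, lists QoL among the secondary end-points of the randomised arm. Under Study procedures, three questionnaires are scheduled for all patients at screening, on the last treatment day and at the first visit about one month later. They are scheduled again at 3, 6, 12 and 24 months, where the list opens with "The following procedures will be done at every follow-up visit".

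Under Statistics, Randomised arm, three populations are defined. Two matter here:

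- "Intent-to-Treat population (ITT) including all patients who were randomised and received at least one fraction of radiation therapy"
- "Per Protocol population (PP) including all patients of the ITT who have received study treatment according to randomisation without significant protocol violations"

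The third is the safety set, which has the same membership as the ITT set but is analysed by treatment received.

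QoL in the randomised arm then gets one sentence: "QoL descriptive analysis will include the subset of the PP patients". No other analysis set is named for it. The observational arm has its own sentence on descriptive QoL statistics, with no PP restriction. The chi-square test of pain response is described without being assigned to any of the three populations.

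**The concern.** Patients are "randomised in a 1:1 ratio" so that the two groups differ only by chance before treatment. PP status is decided later, by what treatment was given and whether a violation counts as significant. Either can depend on the arm and on the patient's condition. Once patients are removed on that basis, a difference in QoL between the remaining groups can reflect who was removed as well as what the treatments did.

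Two features of this trial make uneven removal possible. It is open-label, and the text shown does not define a significant violation. The treatments also differ in complexity. Arm A needs planning CT and MR in immobilisation, two target volumes and daily online position correction, while arm B is 3-dimensional conformal treatment under each centre's own image guidance.

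What is at stake is how a secondary result is read. A by-arm QoL table in a superiority trial will be taken as a comparison of the arms even when it is labelled descriptive.

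**Working it through.** **Plan's own figures.** The plan states no expected QoL mean, standard deviation or PP share, so there is no QoL figure to reproduce. Its sample size concerns pain response: 40% versus 70%, 90% power and 5% two-sided (sidedness is not stated) give 56 per arm, and 56 / (1 − 0.30) = 80. That matches the stated 80 per arm. Nothing below depends on it, except that 80 turns percentages into patients.

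**Does PP membership depend on later events?** It requires that patients be ones "who have received study treatment according to randomisation without significant protocol violations". Treatment actually received is a post-randomisation event, and violations can be. So the answer is yes, whatever the prognosis of those excluded.

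**Illustration of size (all inputs assumed).** In one arm let x be the share excluded from PP, m the mean of those retained, and g the number of points by which the excluded score below the retained.

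- Mean of the whole arm = (1 − x)·m + x·(m − g) = m − x·g.
- So the PP mean is too high by x·g.
- Between-arm bias (A minus B) with the same g in both arms = g·(xA − xB).

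Take a 0-100 scale on which higher is better, and g = 20. A positive value favours arm A.

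| Excluded, A vs B | Patients of 80 | Shift in A | Shift in B | Bias |
|---|---|---|---|---|
| 15% vs 5% | 12 vs 4 | 3 | 1 | +2 |
| 5% vs 15% | 4 vs 12 | 1 | 3 | −2 |
| 25% vs 5% | 20 vs 4 | 5 | 1 | +4 |
| 5% vs 25% | 4 vs 20 | 1 | 5 | −4 |
| equal | equal | equal | equal | 0 |

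If g differs between arms, the bias is gA·xA − gB·xB and need not vanish at equal rates. If the excluded score better than the retained, g is negative and every sign reverses.

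**In standard-deviation (SD) units, within one arm.** With 5% to 20% excluded and a gap of 0.3 to 0.8 SD, the shift runs from 0.05 × 0.3 = 0.015 SD to 0.20 × 0.8 = 0.16 SD. As an extreme, suppose the excluded are exactly the worst-scoring share x of a normal distribution. The shift is then φ(z)/(1 − x), with φ the standard normal density and z its x-quantile: 0.11 SD at 5% and 0.35 SD at 20%. The between-arm bias is the difference of the two arms' shifts.

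**The case against.** The strongest case against the point has five parts.

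- **The analysis is descriptive.** No QoL test, effect estimate or interval is planned in the text shown. This stands. The primary conclusion and its type I error are untouched.
- **Those excluded need not be the patients who do worst.** A reader might infer that PP drops patients with toxicity, pain or decline and so flatters both arms. The definition does not say this. Courses are 5 or 10 fractions in either arm, and later deterioration, death or dropout does not by itself remove anyone from PP. Significant violations could be planning or eligibility deviations unrelated to prognosis. This stands too.
- **The direction is open.** A reader might infer a bias towards SBRT because arm A is more complex. In an open-label trial, control patients who received another treatment would equally leave PP, and the sign would reverse. The documents support neither direction.
- **The primary result may use the same population.** A reader might infer that QoL describes different patients from the pain analysis. The Synopsis never assigns the primary test to a set, so this cannot be claimed.
- **PP may not be meant as the only set.** The Synopsis says analysis will be done in three populations, and the SAP, which is not at hand, could add one for QoL. Restriction to PP is still the natural reading. If more was meant, the sentence needs correcting anyway.

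None of this answers the core point. The protocol itself chooses the set, so this is not a detail left open, and the set it chooses is formed after randomisation.

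**Conclusion.** The point holds in limited form. The only analysis set stated for QoL in the randomised arm is selected after randomisation, so the by-arm summary is not a comparison of the groups as randomised, and questionnaires scheduled for the excluded patients go unused. That follows from the definitions and needs no assumption about prognosis.

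The size and sign of any bias cannot be derived from the documents. Under the assumed 20-point deficit it is 2 points in either direction at 15% versus 5% excluded, 4 points at 25% versus 5%, and nil at equal rates with equal deficits. If few patients leave PP, the effect is small. It is worth correcting because the correction is cheap. It does not threaten the primary result.

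**What to change.** Replace the QoL sentence under Statistics, Randomised arm, with a rule to this effect: QoL is summarised descriptively by visit and by randomised arm in all randomised patients, using every available questionnaire. For each visit and arm, the numbers of questionnaires expected and completed and the number of patients deceased are reported. The PP set is shown only as a supportive analysis.

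Two details matter:

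- The set should be all randomised patients, not the protocol's ITT set. That set requires at least one fraction, so it also rests on a post-randomisation condition, though a milder one.
- No post-baseline questionnaire should be required for inclusion, because that would drop patients who die or decline before completing one.

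The change does not cure missing forms. The schedule covers all patients, but completion will be lower: follow-up runs for two years or until death, and the sample size allows for 30% dropout. That is why the counts by visit and arm are needed.

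The cost is one sentence and slightly more reporting work. No new data collection is needed.
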